Specific Aim 1 (human stress study). Determine the temporal relationship between psychological stress, ccf-mtDNA, and systemic inflammation. We hypothesize that socioevaluative stress will trigger robust and transient ccf-mtDNA release compared to a non-stressed condition. To test this, 60 volunteers (50% female; aged 20-50) will be tested on two occasions separated by at least 1 month. On one occasion, they will be exposed to the a socio-evaluative speech stressor known to elicit increases in circulating markers of inflammation at 40-90 minutes. On the other occasion, they will rest quietly for the same period of time. Conditions will be counterbalanced across subjects and blood drawn at ten time points over two hours. We expect that the stress task will induce a specific increase in ccf-mtDNA, which will statistically mediate subsequent peak circulating IL-6 and TNF- α levels. To validate that the stress task was associated with physiological arousal, we will examine task-related changes in heart rate, blood pressure, heart rate variability, and circulating levels of cortisol, epinephrine, and norepinephrine. This study will establish the kinetics and magnitude of psychological stress-induced ccf-mtDNA release, and whether ccf-mtDNA mediates the inflammatory response to acute stress in humans.

Study Design & Methods

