We propose a crossover experimental trial examining physiological responses to a socio-evaluative speech task under laboratory conditions. Participants will be tested on two occasions separated by at least 1 month. On one occasion, they will be exposed to the speech task. On the other occasion, they will rest quietly for the same period of time with identical assessment in the absence of the stressor. This control session will allow us to assess and control for any possible effects of the passage of time (e.g., circadian variation in cortisol levels), simply being assessed (e.g., discomfort), and the intravenous catheter. Conditions will be counterbalanced in randomized starting order across subjects and blood drawn at ten time points over two hours to assess ccf-mtDNA, markers of inflammation (IL-6 and TNF- α), and levels of cortisol, epinephrine and norepinephrine. Heart rate (HR), blood pressure (BP), and heart rate variability (HRV) will be assessed as indices of autonomic activation before, during and after the stressor. The speech task is a widely used, highly effective way to investigate stress responses in a laboratory setting. It induces significant increases in cortisol, indices of autonomic activation, and circulating IL-6 and TNF α . Our preliminary data provides novel evidence that this stressor also results in increased cc-mtDNA, which may mediate the increases in circulating levels of IL-6 and TNF- α that peak 40-90 minutes post-stress.

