visit will be rescheduled. Participants who have taken non-steroidal anti-inflammatories in the past 24 hours will also be rescheduled. If they pass these screenings, standby participants will be confirmed to come in if the primary participant has to be rescheduled.

Participants will attend two laboratory visits at the Behavioral Physiology Laboratory, University of Pittsburgh, scheduled at least one month apart. The first visit will last approximately 4 hours and the second visit approximately 3.5 hours. Both visits will be scheduled in the afternoon starting between 1 and 3 pm to control for diurnal variation in the biological measures of interest. Participants will be asked to avoid eating or drinking anything except water from 12pm on both days of testing. At the first visit, the project coordinator will meet with the volunteer to explain the study and obtain written informed consent according to the University of Pittsburgh Institutional Review Board guidelines.

Following consent, the research nurse will conduct a medical history and medication use screen, and record the participants resting heart rate, blood pressure, height, weight, and body fat. In the event that participants are identified who are ineligible for the study (e.g., due to exclusionary medical or psychiatric conditions or taking excluded medications, with a resting blood pressure $>140/90$, weight < 110 lbs or BMI equal to or greater than 30), they will be excused from the study at this point.

Next, the blood eligibility assessment will be repeated to confirm that the participant adhered to pre-visit instructions (e.g., no non-prescription medications in the prior 2 days) and did not present with new symptoms of upper respiratory infection. In the event that they are no longer eligible for the blood draw that day, the visit will be rescheduled. Participants who are eligible for the blood draw will next complete demographic questionnaires on the computer. It is estimated that these questionnaires will take 30 minutes to complete.

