Univariate and descriptive analysis will be performed on all dependent variables and, if necessary, normalizing and/or variance stabilizing transformations will be applied to the data before inferential analyses are undertaken. All hypothesis testing will involve two-sided alternative hypotheses with the α level set to 0.05. The analytic strategy for addressing Aim 1 will involve fitting linear mixed models, which allow flexible covariance structures to account for correlation of repeated measures data. Specifically, subject and day (nested within subject) will be the random effects, and condition (stress/control) along with other covariates will be the fixed effects. We will also include time and time 2 (squared) as fixed effects to allow for a nonlinear response. The outcome variables will be the various physiological and psychological responses:

IL-6, TNF- α , ccf-mtDNA, cortisol, epinephrine, norepinephrine HR, BP, momentary negative affect, and HRV.

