## Statistical Plan and Power

Power: For the primary analysis, because we are utilizing a “matched” design (in which each subject serves as his/her own control), we based our power calculations on a simple paired t-test since power formulas are not available for complex models such as the ones we propose to apply to our data. We determined that with the sample size  $n = 60$ , we would have 80% power to detect a normalized difference (in terms of Cohen’s  $d$ ) as small as 0.38. Combined effects sizes from a meta-analysis of the literature [1] yield normalized effect sizes for IL-6 and TNF- $\alpha$  at 0.35 and 0.28, respectively. For ccf-mtDNA, our pilot data gave an estimated effect size of 1.13. Thus, with a sample of  $N=60$ , we were sufficiently powered to detect stress-induced changes. In fact, the collection and modelling of multiple measurements over time. With multiple observations, accounting for the correlation structure among repeated observations, we would increase the power of the analysis to detect a change.

Univariate and descriptive analysis will be performed on all dependent variables and, if necessary, normalizing and/or variance stabilizing transformations will be applied to the data before inferential analyses are undertaken. All hypothesis testing will involve two-sided alternative hypotheses with the  $\alpha$  level set to 0.05. The analytic strategy for addressing the laboratory stress session will involve fitting linear mixed models, which allow flexible covariance structures to account for correlation of repeated measures data. Specifically, subject and day (nested within subject) will be the random effects, and condition (stress/control) will be the fixed effects. We will also include time and time $^2$  (when indicated) as fixed effects to allow for a nonlinear response. The outcome variables will be the various physiological and psychological responses: IL-6, TNF $\alpha$ , ccf-mtDNA, cortisol, epinephrine, norepinephrine HR, BP, momentary negative affect, and HRV.

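### The two-visit crossover model has no fixed visit (period) effect, although visits 1 and 2 differ by design

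*SAP*

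**What the plan says.** The Protocol (Study Design & Methods) describes the design in these words: "We propose a crossover experimental trial examining physiological responses to a socio-evaluative speech task under laboratory conditions". Study Objectives gives the size and spacing: "To test this, 60 volunteers (50% female; aged 20-50) will be tested on two occasions separated by at least 1 month". On order, the Protocol says: "Conditions will be counterbalanced in randomized starting order across subjects". It does not give the number per order, any blocking, or what happens when a participant misses the second visit.

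The SAP (Statistical Plan and Power) specifies the model: "subject and day (nested within subject) will be the random effects, and condition (stress/control) will be the fixed effects". Time is added, and time squared when indicated, to allow a curved response; this is time within a session, not the visit. The Protocol (Statistical Considerations) gives the same model plus further covariates that it does not name. The SAP leaves those covariates out. Neither text names visit, period or order.

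The visits are not alike. The Protocol says: "The first visit will last approximately 4 hours and the second visit approximately 3.5 hours". Consent, the nurse's history and measurements, and about 30 minutes of questionnaires are described in the first-visit sequence, before the catheter is placed.

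**The concern.** In a two-period crossover each person's stress-minus-rest difference contains the stress effect plus or minus the visit 2 minus visit 1 shift, with the sign set by order. A fixed visit term estimates that shift and takes it out. A random day-within-subject term cannot, because it is centred at zero: a shift common to all participants appears as extra day-to-day variance. As written, the model has no condition × time term and no baseline covariate, so the condition effect is the between-day contrast that carries the shift.

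There are reasons to expect a shift. Visit 1 is the first exposure to the laboratory and the catheter. Both visits start between 1 and 3 pm with only water from noon, so the longer preparation at visit 1 plausibly puts sampling later in the day and after a longer fast. The Protocol itself names passage of time, being assessed and the catheter as influences that the rest session should control. It does so fully only if they act equally at both visits, or if visit is in the model.

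Two things are at stake: precision when the two orders are equal in number, and bias when they are not.

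**Working it through.** **Inputs from the documents.** N = 60. Test level: "All hypothesis testing will involve two-sided alternative hypotheses with the α level set to 0.05". Power statement: "we would have 80% power to detect a normalized difference" (Cohen's d) "as small as 0.38", from a paired t-test. Expected effects: 0.35 (IL-6), 0.28 (TNF-α), 1.13 (ccf-mtDNA).

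**Assumptions.** The documents give no visit shift and no order split. I take π, the visit 2 minus visit 1 shift in SDs of the paired difference, as 0.5 (range 0.25 to 0.75), and orders of 30/30 or 33/27.

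**1. The plan's own figure.** Paired t, noncentrality d√n = 0.38 × √60 = 2.94, 59 df: power is 82.5%, and the detectable d at 80% power is 0.368. The stated 80% at 0.38 is slightly conservative. This does not bear on the present point. On the same basis power is 76.0% at 0.35, 56.9% at 0.28 and above 99.9% at 1.13.

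**2. Model for the differences.** D = d + sπ + e, where e has SD 1, s = +1 if stress is at visit 2 and −1 if it is at visit 1.

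**3. Equal orders, no visit term.** There is no bias. The estimated SE is inflated by √(1 + π² × 60/59); at π = 0.5 this is √(1 + 0.25 × 1.017) = 1.120. The sum of squares of D is noncentral chi-square with 59 df and noncentrality 60π², while the mean keeps its true variance of 1/60. The t-test is therefore conservative:

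| π | SE inflation | Power, d = 0.35 | Power, d = 0.28 | True type I error |
|---|---|---|---|---|
| 0 | 0% | 76.0% | 56.9% | 5.0% |
| 0.1 | 0.5% | 75.7% | 56.5% | 4.9% |
| 0.25 | 3% | 74.1% | 54.5% | 4.3% |
| 0.5 | 12% | 68.1% | 47.5% | 2.9% |
| 0.75 | 25% | 58.2% | 37.3% | 1.5% |

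Simulation with 40,000 trials per scenario agrees to within about one point.

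**4. Unequal orders, no visit term.** Bias = π × (n stress second − n stress first)/N. At 33/27 and π = 0.5 this is 0.5 × 6/60 = 0.05 SD (0.025 at π = 0.25; 0.075 at π = 0.75). Against an effect of 0.35 that is 0.05/0.35 = 14%. At 36/24 and π = 0.5 the bias is 0.5 × 12/60 = 0.10 SD and type I error is about 8%. If order were assigned by simple randomisation, the chance of a split of 33/27 or worse among 60 is 52%, and of 36/24 or worse 15.5%. Blocking would reduce this, but drop-out could bring it back.

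**5. With a visit term.** Effective n = 4 × n1 × n2/N, with 58 df. At 30/30, power is 76.0% (d = 0.35) and 56.9% (d = 0.28) whatever π is. At 33/27, effective n = 4 × 33 × 27/60 = 59.4, and power is 75.6% and 56.4%. The bias is zero.

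**6. Check in the mixed model itself.** A small simulation (15 data sets per scenario, ten samples per visit, SD of the paired difference 0.877, shift 0.44, so π = 0.50) gave at 30/30 a mean SE of 0.121 without the visit term and 0.110 with it. At 36/24 the two estimates differed by 0.092; the formula gives 0.44 × 12/60 = 0.088.

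**The case against.** The strongest reply is that the size is unknown and may be small. No visit effect is reported, and at π of 0.2 or less with near-equal orders the loss is about one to two points of power. That stands, and the power figures are illustrative.

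Second, ccf-mtDNA, the outcome at the centre of the Aim 1 hypothesis, keeps power above 99.9% at every shift considered. That also stands. The case for a shift is strongest for cortisol, catecholamines, heart rate, blood pressure and mood, while the power figures are for IL-6 and TNF-α. For those two the argument is weaker but not absent: the Protocol fixes the afternoon start to control diurnal variation in its biological measures.

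Third, the design limits the problem. Order is randomised, so the bias averages to zero over repeated trials, and both visits have a 30-minute habituation period before the first sample. This reduces the shift but does not show that it is nil, and a bias that averages to zero can still affect the one trial that is run. At 33/27 with π = 0.5 type I error is about 4%, still below 5%; inflation needs a larger imbalance.

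Fourth, a constant visit shift cancels from a change-from-baseline contrast. That is true, but the stated model contains no such contrast. A visit difference that varies over the session would not cancel either.

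Last, the Protocol's unnamed covariates could include visit. Nothing says so, and the SAP omits them.

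**Conclusion.** The concern holds. The SAP's stated model leaves out the period term that a two-period crossover needs, and random day does not replace it. With equal orders the consequence is lost precision and a conservative test, not bias. With unequal orders the stress estimate also takes on a fraction of the visit shift equal to the imbalance divided by N. At an assumed shift of 0.5 SD the cost is about 8 to 9 points of power for IL-6 and TNF-α, or 0.05 SD of bias at 33/27. Both inflammatory effects already lie below the plan's detectable 0.38, so there is no precision to spare. The conclusion about ccf-mtDNA power does not change. All sizes depend on the assumed shift and order split; the structural point does not.

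**What to change.** In the SAP (Statistical Plan and Power) and the Protocol (Statistical Considerations), add visit (1 or 2) as a fixed effect, together with visit × time, in every mixed model for the listed outcomes. State the number analysed in each order when reporting.

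This takes one sentence in each document and no new data, since visit order is known for every participant. The condition contrast loses one degree of freedom (59 to 58), about 0.02 percentage points of power at 30/30. The visit × time terms use further degrees of freedom from the repeated samples; their effect on power was not calculated here. The change uses the order that the trial already randomises.
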